1.4.2 SAFETY VISITS AND MONITORING REQUIREMENTS

Timing of post-randomisation safety tests (bloods, urine, blood pressure and safety assessment) are shown in the main protocol schedule of events (Table 1, section 2 Trial Design), and in the drug-

specific schedule of events at the beginning of each drug-specific appendix. Further details, including the exact laboratory tests required, are provided below.

1.4.2.1 SAFETY VISITS (IN ADDITION TO MAIN TRIAL VISITS)

No additional safety visits are required for participants randomised to dupilumab at the start of the trial. For participants who switch on to dupilumab at 6 months a safety assessment (no bloods needed, can be remote) is required at week 30. Participants who switch from dupilumab to methotrexate at 6 months will require a pregnancy test. In the event of dose reduction, additional safety assessments should be arranged at the discretion of the investigator.

1.4.2.2 SAFETY BLOODS

The following safety bloods will be performed at weeks 13, 26 and 52:

HAEMATOLOGY Haemoglobin Haematocrit Total and differential leukocyte count Red blood cell count Platelet count

BIOCHEMISTRY Creatinine Potassium Liver function tests (LFTs)

1.4.3 MANAGING TOXICITY WITH DUPILUMAB

Dupilumab is licensed for use in this study population (adults with moderate to severe eczema). Investigators should refer to the relevant summary of product characteristics in the event of toxicity.

1.4.4 EVALUATING AE'S AND SAE'S – ASSESSMENT OF EXPECTEDNESS

Section 4.8 of the following SmPC's form the RSI for dupilumab for this trial: Dupixent 300mg prefilled pen SmPC (dated 09/09/2024); Dupixent 300mg pre-filled syringe (dated 09/09/2024). These can be found in investigator site files (SmPC & Safety Alert Updates).

1.5 **REFERENCES**

APPENDIX 4 DRUG-SPECIFIC INFORMATION: ABROCITINIB

TRIAL PARTICIPANT FLOW AND SCHEDULE OF EVENTS: ABROCITINIB

ABROCITINIB SCHEI	DULE O	FEVE	NTS					
Event / form	Screening	Baseline ^A	Week 4 (Month 1)	Week 13 (Month 3)	PRIMARY OUTCOME Week 26 (Month 6)	Week 39 (Month 9)	Week 52 (Month 12) End of Study Visit	Ongoing
Informed Consent	Х							
Registration Form	X							
Eligibility (confirmation only at baseline)	Х	Х						
Medical History and demographics	X							
Skin photography (optional)		X			X			
Randomisation Form (after all baseline data collected)		Х	N/	v	X			
Status Form	v	v	X	X	X	X	X	
Physical examination [*]	X	X	X	X	X	X	X	
Blood pressure	X	X					-	
Orinalysis Brognopou toott	^	v						
Eczema Area and Severity Index (EASI)		^						
BLINDED ASSESSOR		х	Х	Х	X	Х	Х	
Investigator Global Assessment (vIGA-AD)		х	х	x	х	х	х	
BLINDED ASSESSOR		v	v	v	v	v	v	
Peak pruritus pumerical rating scale (NRS)		Ŷ	× ×	Ŷ	Ŷ	× ×	Ŷ	_
Eczema control (RECAP)		Ŷ	X	Ŷ	X	X	X	
Patient global assessment (PtGA)		X	X	X	X	X	X	-
Dermatology Life Quality Index (DLQI)		X	X	X	X	X	X	
		X	~	X	X	X	X	
PHQ-9		X		~	X		X	
GAD-7		X			X		X	
Resource use		X		Х	X	Х	X	
Adherence check (VAS) & Tolerability				Х	Х	Х	Х	
Participant Online Surveys		Х					Х	
Dispense medication		Х		Х	Х	Х		
Screening blood tests (+DNA for filaggrin status,	x							
optional)	^							
Safety Blood Tests (can be remote)		Х	X	X	X		X	
Study medication switch review				v	X	v		
Study medication dose increment review				X		X	 	V
Concomitant Medications Log		v	v	v	v			×
Adverse Events Log		^	^	^	^		 	v
Withdrawal Form							 	Ŷ
* Physical examination (according to routine clinical care) require	ed at sci	reening	and ba	seline	extent of	physical	exam du	rina
follow up as deemed appropriate by investigator				.,				9

* Women of childbearing potential only. Urine test

A: Baseline safety bloods for all treatments, at investigator discretion based upon timing of screening bloods

Please note: if IMP is switched at 6 months, the schedule of events for the second IMP must be followed for the second 6 months of the trial.

CONTENTS

1	ABRC	OCITINIB-SPECIFIC INFORMATION	101
	1.1	BACKGROUND	101
	1.1.1	Background and mechanism	101
	1.1.2	Rationale for use of abrocitinib	101
	1.1.3	Abrocitinib dose justification	101
	1.1.4	Rational for 6 month switch option for those who do not respond to abrocitinib (methotrexate) .	101
	1.2	ABROCITINIB TOXICITY AND SAFETY	102
	1.2.1	Common side effects	102

1 ABROCITINIB-SPECIFIC INFORMATION

1.1 BACKGROUND

1.1.1 BACKGROUND AND MECHANISM

Abrocitinib is a Janus kinase (JAK) inhibitor. Cytokines that are integral to the pathogenesis of atopic eczema, including IL-4, IL-13, IL-31 and IL-22, require effective janus kinase activity to exert their effects. Binding of the cytokines to their extracellular receptors induces cross-phosphorylation of JAKs, facilitating STAT binding and subsequent downstream signalling (JAK-STAT pathway). The JAK family comprises four enzymes, JAK1, JAK2, JAK3 and TYK2. The key cytokines relevant to atopic eczema all require JAK1 function. Abrocitinib is significantly more selective for JAK1 than JAK2, JAK3 or TYK2 and has proven effective in treating atopic eczema¹.

1.1.2 RATIONALE FOR USE OF ABROCITINIB

Janus kinase inhibitors are a new class of treatment for atopic eczema offering a different mechanism of action to the previously available options. They have demonstrated effectiveness in trials^{2,3} and are increasingly used in practice. The aim of BEACON is to integrate such novel and efficacious treatments into the platform to get head-to-head comparative data against existing therapies. Like dupilumab, no JAKi have been compared against the existing 'standard' treatments including methotrexate and ciclosporin. The more JAK1 specific agents (e.g. abrocitinib and upadacitinib) have proven most effective in trials (more effective than baricitinib), with the top dose of abrocitinib and upadacitinib showing similar levels of effect (measured by absolute change in EASI) in a current living network meta-analysis (effect sizes compared with dupilumab: 2.2, 95% CI 0.2-0.4 and 2.7, 95% CI 0.6-4.7, respectively)⁴. Abrocitinib has been chosen as a JAK class exemplar to enter BEACON (unless clear reason we would not aim to integrate more than one treatment from the same mechanistic class). See main protocol sections 1.1.1 and 1.4 for further background information.

1.1.3 ABROCITINIB DOSE JUSTIFICATION

Abrocitinib is licensed for the treatment of moderate to severe eczema in adults and comes in two available doses, 100mg or 200mg daily. As per license, the lower dose is recommended for people in whom there are risk factors (e.g. those at higher risk of venous thrombo-emobolism (VTE), major adverse cardio-vascular events (MACE) or malignancy) whereas the higher dose may be more appropriate for those without risk factors and with a high disease burden (see abrocitinib SmPC). Given the population entering this study (moderate-severe eczema requiring systemic treatment, i.e. high burden), that people with relative contraindications to the treatment would unlikely be put forward for randomisation to this arm, and the superior effect of higher dose treatment over lower dose treatment in trials we have elected to start participants on 200mg of abrocitinib². This is in line with current clinical practice and the dose can be reduced at any stage in the trial at the discretion of the investigator.

1.1.4 RATIONAL FOR 6 MONTH SWITCH OPTION FOR THOSE WHO DO NOT RESPOND TO ABROCITINIB (METHOTREXATE)

For those participants on abrocitinib who do not meet response criteria to continue at 6 months they can switch to methotrexate. Methotrexate was chosen because it represents the most commonly prescribed first line systemic treatment for atopic eczema in the UK, it can be safely continued beyond 12 months (unlike ciclosporin), there would be no funding issue preventing continuation post-trial and it has a more contrasting mechanism of action compared to other novel agents. This will

also provide novel information on the sequential benefit of switching from abrocitinib to methotrexate and would mean that participants would be eligible to move on to a more novel agent post-trial (e.g. dupilumab) if needed.

1.2 ABROCITINIB TOXICITY AND SAFETY

Administration of abrocitinib for this study is not anticipated to induce any potential risk other than the known potential side effects listed below (see SmPC).

1.2.1 COMMON SIDE EFFECTS

Nausea; abdominal pain; vomiting; herpes simplex (including oral, ophthalmic, genital and eczema herpeticum); herpes zoster (including ophthalmic); headache; dizziness; acne; creatinine phosphokinase increase.

1.2.2 UNCOMMON SIDE EFFECTS

Pneumonia; thrombocytopaenia; lymphopenia; hyperlipidaemia (including dyslipidaemia and hypercholesterolaemia); venous thromboembolism (including pulmonary embolism and deep vein thrombosis).

1.2.3 DRUG INTERACTIONS

Investigators should check for any relevant drug interactions in the abrocitinib SmPC.

1.2.4 POST-TREATMENT CONTRACEPTION REQUIREMENTS

Females need to continue effective contraception for 1 month after stopping abrocitinib.

1.3 SELECTION OF PARTICIPANTS

1.3.1 PARTICIPANT CORE INCLUSION AND EXCLUSION CRITERIA

To be eligible for randomisation, all participants must fulfil the core inclusion criteria and none of the exclusion criteria stated in section 5.3 of the main protocol in addition to the arm-specific criteria below.

Please note, as long as a participant is eligible to take ciclosporin (control arm) and at least one of the other trial treatments they can be randomised (i.e. they can meet exclusion criteria for one or more of the other treatments and still be randomised). If they fail to respond at 6 months, a pre-defined treatment switch (as per protocol) may or may not be possible depending on whether they still meet exclusion criteria for the relevant switch option. If the switch is not possible, they would be withdrawn from the trial at that stage.

1.3.2 ABROCITINIB-SPECIFIC EXCLUSION CRITERIA

In addition to the core inclusion and exclusion criteria documented in the main protocol, the following arm-specific exclusion criteria apply for the abrocitinib arm.

1. Any contraindication to abrocitinib according to standard clinical care and/or the opinion of the investigator.

Note, as per license, abrocitinib should only be used if no suitable treatment alternatives are available in patients:

- 65 years of age and older

- patients with history of atherosclerotic cardiovascular disease or other cardiovascular risk factors (such as current or past long-time smokers);

- patients with malignancy risk factors (e.g. current malignancy or history of malignancy)

Note, the need for a shingles vaccination (Shingrix) should be considered based on any specific risk factors relevant to the individual participant and up to date formal Green Book guidance: Immunisation against infectious disease - GOV.UK (www.gov.uk).

Please note: in relation to main exclusion criteria point 2 (main protocol section 5.3), systemic therapies in the same class as abrocitinib would, for example, include baricitinib and upadacitinib.

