5.3.2 EXCLUSION CRITERIA

- 1. Active dermatologic conditions that may confound the diagnosis of atopic eczema or interfere with assessment of treatment.
- 2. Prior exposure to any of the systemic therapies being investigated in the trial or those with a similar mechanism of action to the systemic therapies being investigated in the trial (see drug specific appendices for examples of excluded drugs and further information).
- 3. Receipt of any of the following:
 - a. Phototherapy (UVB TL01, UVB, PUVA, UVA1), tanning beds, oral or parenteral traditional Chinese medicine or oral systemic immunosuppressant/ immunomodulatory agent that can help eczema (including but not limited to prednisolone, azathioprine, mycophenolate mofetil, tacrolimus, Janus kinase (JAK) inhibitor or phosphodiesterase 4 inhibitor) within 4 weeks prior to randomisation.
 - b. Biologic therapy for eczema (including but not limited to amlitelimab, rocatinlimab and nemolizumab) within 3 months prior to randomisation.
 - c. Receipt of a cell-depleting agent (e.g. rituximab, alemtuzumab, cyclophosphamide, chlorambucil) for 6 months prior to randomisation or until lymphocyte count returns to normal (whichever is longer)
- 4. Any medical condition that, in the opinion of the investigator, may compromise the safety of the participant in the trial, interfere with evaluation of the IMP, or reduce the participant's ability to participate in the trial.
- 5. Receipt of live/ live attenuated vaccine 30 days prior to the baseline visit date or expected need of live / live attenuated vaccination during the trial.
- 6. Participating in another clinical trial.
- 7. Women of child-bearing potential (WOCBP*) at risk of pregnancy during the trial (i.e. sexually active women not on effective contraception **)
- 8. Women who are pregnant or breastfeeding.

* WOCBP defined as: fertile, following menarche and until becoming post-menopausal unless permanently sterile. Permanent sterilisation methods include hysterectomy, bilateral salpingectomy and bilateral oophorectomy. A postmenopausal state is defined as no menses for 12 months without an alternative medical cause.

**Effective methods of contraception include:

- combined (oestrogen and progestogen containing) hormonal contraception associated with inhibition of ovulation:
 - oral
 - intravaginal
 - transdermal
- progestogen-only hormonal contraception:
 - oral
 - injectable
 - implantable
- o intrauterine device (IUD)

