5.3.3 DRUG-SPECIFIC EXCLUSION CRITERIA

See the individual drug appendices for the additional drug-specific exclusion criteria. **Please note**, as long as a participant is eligible to take ciclosporin (control arm) and at least one of the other trial treatments they can be randomised (i.e. they can meet exclusion criteria for one or more of the other treatments and still be randomised). If they fail to respond at 6 months, a predefined treatment switch (as per protocol) may or may not be possible depending on whether they still meet exclusion criteria for the relevant switch option. If the switch is not possible, they would be withdrawn from the trial at that stage.

5.4 **INFORMED CONSENT**

Informed consent will be obtained by the Principal Investigator or delegated physician at each site, following personal explanation of the trial procedures. If a participant is physically unable to sign the consent form, verbal consent in the presence of a witness can be documented on the consent form and the participant signature should be marked with an X. The following text should be written on the form: 'Participant physically unable to sign consent but has given verbal consent in the presence of [name, relationship to clinic or participant, contact information]'. The witness should sign the witness line on the consent form and the physician should sign the consent form as normal. Participants who lack capacity to provide verbal consent are not eligible to participate.

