13.2 LONG-TERM HEALTH-ECONOMIC ANALYSIS

A disease-based decision-analytic model will be developed to evaluate the expected long-term costs and health consequences of moderate to severe eczema in adults. This will incorporate periods of disease relapse and remission, adverse events related to treatment and drug specific prescribing guidelines (e.g. ciclosporin use not recommended for >1 year). Sensitivity analysis will be used to explore assumptions made (i.e. about treatment duration, costs, disease severity and relapse rates post-treatment). The model form is likely to be a Markov-type model, where groups of patients move between defined health states (e.g. healthy skin, mild eczema, moderate eczema, severe eczema, death) using estimated probabilities of disease progressions for fixed time intervals. Model design will be finalised after: a) an updated review of existing eczema economic models⁴⁶; b) multidisciplinary input on model structure and data sources; and c) review of evidence for source data for model parameters. This process will be documented to interrogate the proposed model and reach agreement amongst those involved. Identification, selection and synthesis of relevant evidence sources will follow recommended methods and will use the primary data collected within BEACON and expert clinical input amongst the team. The Markov model will be developed in an open-source framework (excel/visual basic/R) to enable sharing. To demonstrate model credibility we will ensure transparency, face validity, internal validity (including sensitivity analysis using a broad range of values for all parameters to ensure the model behaves as expected according to the theoretical model) and model corroboration (a discussion of similarities and differences between the model produced and those already in the literature). An economic evaluation will be performed for an appropriately long-time horizon in line with the within trial analyses except all costs and benefits will be discounted at recommended rates to reflect the longer timeframe.

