1.1.3 DUPILUMAB DOSE JUSTIFICATION

Dupilumab has one standard licensed dose for the treatment of adults with moderate to severe eczema, which has been utilised in this trial.

1.1.4 RATIONALE FOR 6 MONTH SWITCH OPTION FOR THOSE WHO FAIL TO RESPOND TO DUPILUMAB (METHOTREXATE)

For those participants on dupilumab who do not meet response criteria to continue at 6 months they can switch to methotrexate. Methotrexate was chosen because it represents the most commonly prescribed first line systemic treatment for atopic eczema in the UK, it can be safely continued beyond 12 months (unlike ciclosporin), there would be no funding issue preventing continuation post-trial and it has a more contrasting mechanism of action compared to other novel agents (e.g. JAKi). This will also provide novel information on the sequential benefit of switching from dupilumab to methotrexate and would mean that participants would be eligible to move on to a more novel agent post-trial (e.g. JAKi) if needed.

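### Appendix 4 reports that the licence recommends the lower abrocitinib dose for people with risk factors, yet the written starting dose is 200 mg for the whole arm

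*Protocol*

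**What the plan says.** **Dose.** Appendix 4, 1.1.3 names two licensed doses, 100 mg and 200 mg daily. It reports that "the lower dose is recommended for people in whom there are risk factors", and gives as examples "those at higher risk of venous thrombo-emobolism (VTE), major adverse cardio-vascular events (MACE) or malignancy". The higher dose is described as possibly more suitable for people with a high disease burden and no risk factors. The section then chooses 200 mg as the start. Its reasons are the high burden of the trial population, the better effect of the higher dose in trials, and the expectation that "people with relative contraindications to the treatment would unlikely be put forward for randomisation to this arm". It adds that the investigator may lower the dose later. The dose line in 1.4.1 and the intervention list in the synopsis both give 200 mg daily without exception.

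**Eligibility.** Appendix 4, 1.3.2 has one numbered exclusion: any contraindication to abrocitinib under standard care or in the investigator's opinion. A note beneath it says that, under the licence, "abrocitinib should only be used if no suitable treatment alternatives are available in patients" aged 65 or over, with cardiovascular disease or risk factors, or with malignancy risk factors.

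**Reduction.** Section 2 allows dose reduction at any time when clinically indicated. Appendix 4, 1.4.1 describes both the 100 mg and the 200 mg tablet.

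**The concern.** The protocol states what the licence recommends for people with risk factors and then writes a starting dose that departs from it, with no rule for a person with a risk factor who is nevertheless included. An investigator who follows the text starts that person on 200 mg and considers afterwards whether to reduce. The matter at stake is participant safety: Appendix 4, 1.2.2 itself lists venous thromboembolism among the drug's uncommon side effects. There is also a consistency cost, because some investigators would reduce early and others would not.

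**Working it through.** No arithmetic decides this point, so the texts are set side by side and one participant is followed through them.

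1. **Dosing as the protocol reports the licence (Appendix 4, 1.1.3).** Risk factors present: the lower of the two doses, 100 mg. No risk factors and high burden: 200 mg may suit better.

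2. **Dosing as the protocol sets it (1.1.3, 1.4.1, synopsis).** 200 mg at the start, for all. Rules 1 and 2 agree only if nobody with such a risk factor enters the arm.

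3. **Does anything guarantee that?**
   - *Core exclusion 4 (Section 5.3.2)* removes people whose medical condition may, in the investigator's opinion, compromise their safety. It is a judgement, made case by case.
   - *The numbered exclusion in 1.3.2* removes people with a contraindication, again by standard care or opinion. A factor that calls for a lower dose is not automatically a contraindication; the licence as reported foresees treating such people at 100 mg.
   - *The note in 1.3.2* is conditional and covers age, cardiovascular risk and malignancy risk. Thromboembolic risk is not named.
   - *The expectation in 1.1.3* is a forecast about referral, not a rule.

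4. **Does dose reduction close the gap?** No. It is discretionary and, as written, acts on someone already taking 200 mg. Appendix 4, 1.4.2.1 leaves extra safety assessments after a reduction to the investigator, but no section provides a 100 mg start.

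5. **A participant traced through the text.** Take an adult under 65 at raised thromboembolic risk, with no cardiovascular or malignancy risk factor, eligible for ciclosporin, whose risk the investigator judges acceptable. Nothing in steps 3 or 4 keeps this person out of the arm or changes the start. The written dose is 200 mg, while 1.1.3 says the licence recommends the lower one.

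6. **Scale.** The arm is 134 of 536 planned participants (synopsis), 134/536 = 1/4. If a share *p* of the arm has such a risk factor, 134 × *p* people are affected. The protocol gives no *p*. Purely for scale, an assumed 5% gives 134 × 0.05 = 6.7 people and an assumed 10% gives 134 × 0.10 = 13.4.

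7. **Effect on the comparison.** Section 12.3 restricts each pairwise comparison to contemporaneously randomised people with no contraindication to either drug. The starting dose, whether uniform or set by baseline risk, is part of the allocated treatment. Neither rule biases the abrocitinib–ciclosporin contrast.

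**The case against.** The strongest reply is that few people, perhaps none, will reach the gap. A doctor must assess eligibility (Section 5.3). Core exclusion 4 and the numbered exclusion in 1.3.2 allow anyone of concern to be kept out, and 1.1.3 describes such people as having relative contraindications. Since everyone must be eligible for ciclosporin, the natural reading of the note is that an alternative exists and the abrocitinib arm is closed to the groups it names; they are randomised among the other 4 − 1 = 3 arms, subject to their eligibility for those. The choice of 200 mg was reasoned, and reduction is available.

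Most of this stands, and it is why the point is modest. What remains is that these safeguards rest partly on judgement, that the note does not name every group for which 1.1.3 reports a lower-dose recommendation, and that the protocol gives no lower start for anyone who is properly admitted.

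A second reply is that a 100 mg start changes the tested regimen. That is true for the people concerned and is a real cost. But the regimen already permits reduction to suit the individual, and for these people the protocol's own account of the licence points to the lower dose.

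**Conclusion.** The point holds as a safety improvement worth making. For anyone included with a licence risk factor, the written start is twice the dose that 1.1.3 says is recommended (200/100 = 2). The number affected is unknown and probably small, given the safeguards above. The conclusion takes the licence only as the protocol describes it.

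Three stronger readings are tempting, and the documents do not support them.

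- *That the note in 1.3.2 cannot be applied because ciclosporin eligibility is mandatory.* As set out above, the natural reading closes the arm to the named groups. The remarks that might suggest ciclosporin is unsuitable ("ciclosporin use not recommended for >1 year" in Section 13.2, and the reason for switching to methotrexate in Appendix 3, 1.1.4) concern long-term modelling and use beyond 12 months. Neither addresses suitability at baseline, and trial treatment lasts at most 1 year.
- *That the risk lists in 1.1.3 and 1.3.2 contradict each other.* The first is offered as examples and concerns dose; the second concerns restriction of use. They need not match. The absence of thromboembolic risk from the note matters only because the note then cannot be relied on to keep such people from a 200 mg start.
- *That the treatment comparison is biased.* It is not, for the reason in step 7 of the working.

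**What to change.** Add to Appendix 4, 1.1.3 and 1.4.1, and to the abrocitinib line of the synopsis: *Participants included with a risk factor for which the SmPC recommends the lower dose start on 100 mg daily; all others start on 200 mg.* Tying the rule to the SmPC avoids maintaining a separate list in the protocol.

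The eligibility text in 1.3.2 can stay as it is. In particular, investigators should not be asked to record that the other trial drugs are unsuitable before opening the arm, because the same person could then be allocated to one of those drugs.

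The cost is low. Comorbidities and smoking history (Section 6.3.3) and age (Section 6.3.4) are already collected before randomisation, the 100 mg tablet is already described, and reduction is already allowed. Sites would need 100 mg stock at baseline. The scientific cost is that an unknown, probably small, share of the arm starts on 100 mg, so the arm estimates the effect of licence-based dosing and not of a 200 mg start for all. Reporting the number started on each dose would make this visible.
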